## 3.3.2 Intermittent fasting

- Induction (1 month) and maintenance (5 months) of a 16:8 intermittent fasting regime (time restricted feeding). During the introductory month, women will only maintain a 14:10 intermittent fasting regime
- Detailed analysis of dietary behaviours and motivation and guidance for induction or maintenance of the intervention at the start of the study and months 2 and months 4 after study initiation
- Dietary guidance at the end of the study to either discontinue intermittent fasting or continue longer-term if desired by participant
- Adjuvant exercise programme

#### 3.3.3 Intermittent fasting with ketogenic supplement

- Induction (1 month) and maintenance (5 months) of a 16:8 intermittent fasting regime (time restricted feeding)
- Detailed analysis of dietary behaviours and motivation and guidance for induction or maintenance of the intervention at the start of the study and months 2 and months 4 after study initiation
- Ketogenic supplement (Kanso MCTfiber, medium-chain triglyceride fiber), provided powderised in a sachet (daily dose) which can be added to food or diluted in water
- Dietary guidance at the end of the study to either discontinue intermittent fasting or continue longer-term
- Adjuvant exercise programme

#### 3.3.4 Exercise programme

The exercise programme is not a key aim of analysis. It is provided to all participants for its general health-promoting effects and includes:

- Analysis of fitness levels at the start of the study (including exercise electrocardiogram)
- Provision of an exercise programme
- Three targeted exercise sessions (resistance, endurance/cardio, flexibility) for motivation and guidance

# 3.4 Quantification of compliance

Participants will be semi-continuously monitored for adherence to the intervention using the following measures:

- Smoking cessation:
  - Reported cigarettes smoked in the last 7 days via personal coaches
  - Urine cotinine levels at month 2, 4, and 6
- Intermittent fasting:
  - Reported compliance with the intermittent fasting regime over the last 7 days via coaches
  - Capillary  $\beta$ -hydroxybutyrate levels throughout the intervention as measured three times a week using FORA6 blood monitoring at home available only for a subset of participants

Adherence to the compliance will also be reported by study doctors at each visit (compliance higher or lower than 75%).

A compliance score will be derived, taking into account the days compliant and the days between the visitations. If a subject reported compliant on all days between two visitations, the compliance score is 100%. Compliance will be cross-checked for concordance

using objective measurements (urine cotinine levels for smoking cessation, and capillary  $\beta$ -hydroxybutyrate levels for the diet intervention). High compliance with smoking cessation should result in no measurable cotinine levels in urine, although the metabolite is only short-lived. High compliance with diet intervention should result in elevated ketone body measurements in capillary blood. As an additional quantitative score of compliance, it may also be measured in number of cigarettes since last visit and cumulative ketone body measures in capillary blood.

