#### Clinical and epidemiological endpoints

- body mass index (BMI), diet arm of the study
- body composition (muscle, fat, water), diet arm of the study
- smoking status, *smoking arm of the study*, including

- current smoking (yes/no)

- cigarettes in the last 7 days
- use of nicotine replacement products
- vascular health

pulse wave velocity, intima-media thickness, and plaque score before and after intervention

- abdominal fat composition, *diet arm of the study* visceral and subcutaneous fat before and after 6 months of intervention
- physical activity and health measured using the international physical activity questionnaire (IPAQ), sports examination (VO2max), and fitness tracker (daily steps, active minutes, floors climbed); resting heart rate
- pulmonary health

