#### 6.4.3 Primary endpoint reporting

For primary endpoint analysis, paired Wilcoxon tests will be performed on adjusted WID scores associated with disease risk, cellular ageing, or exposure, in cervical samples at baseline and month 6 of the intervention (adjusted for immune cell composition). For visualisation, points and lines may be coloured by compliance score, delta BMI, or smoking status at the end of the intervention. Data will be visualised using Spaghetti plots and may additionally be visualised using violin/box plots with overlayed jitter plots.

Analyses will be presented separately per sub-study and a comparison between the two randomised arms in the diet intervention study may be conducted. The analysis is predominantly conducted ITT, but separate subgroup analyses may be conducted as follows:

- $\bullet$  per protocol, if at least 30 individuals have a cumulative compliance score of more than 80%
- diet intervention: timing of fasting, breakfast versus dinner cancellation

Mixed-effects models could provide a complimentary method of reporting individual effects over time.

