#### 6.5.3 Secondary endpoint reporting

Paired analysis (ITT) will be conducted for baseline and month 6 measurements. As with the primary endpoint, PP or above/below median compliance score subgroup analysis may be additionally constructed. Linear-mixed effects models will be constructed to explore heterogeneity in responses among participants and leverage the strength of our longitudinal data. In addition, descriptive statistics relating to change to baseline can be reported. The following outcomes will be assessed:

- body mass index  $(kg/m^2)$ , diet arm of the study
- fat-free body mass (%), diet arm of the study
- current smoking ("yes" or "no", binary response, can be analysed using a generalised estimation equation or generalised linear mixed model with a log link function)
- vascular health parameters
  - pulse wave velocity (mm/s)
  - intima-media thickness (mm)
  - plaque score
- physical activity
  - international physical activity questionnaire (IPAQ) score
  - average daily steps per week
  - active minutes per week
- abdominal fat composition, diet arm of the study
  - visceral fat (mm)
  - subcutaneous fat (mm)
- heart rate variability (ms)
- resting heart rate (beats per minute)
- sleep quality score (fitness tracker, average score per week)
- subgroup in diet arm of the study:  $\beta$ -hydroxybutyrate levels

- pulmonary health, including FEV1, FVC, and FEV1/FVC
- ergonometry functional values

Data will be reported using spaghetti plots (visualising individual values) and/or tables of mean and standard deviations. In the diet arm, changes in body mass index, fat-free body mass, and abdominal fat composition may also be compared between groups (with and without ketogenic supplement) using Wilcoxon testing of delta change, or via inclusion of ketogenic supplement covariate in linear mixed models.

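### Smoking sub-study: per-protocol status is built from reported compliance, and the planned cotinine check has no cut-off, no consequence for a discordant result, and no place in the definition of current smoking.

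*SAP*

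**What the plan says.** **Measures (SAP 3.4).** Adherence to smoking cessation is tracked by "Reported cigarettes smoked in the last 7 days via personal coaches" and by "Urine cotinine levels at month 2, 4, and 6". Study doctors also rate adherence at each visit as above or below 75%.

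**Score (SAP 3.4).** The compliance score uses the days compliant and the days between visits: "If a subject reported compliant on all days between two visitations, the compliance score is 100" per cent. An optional quantitative alternative, the number of cigarettes since the last visit, is also a count of cigarettes and not a cotinine value.

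**Role of cotinine (SAP 3.4).** "Compliance will be cross-checked for concordance" against objective measures, cotinine being the one for smoking. The expected result is given: "High compliance with smoking cessation should result in no measurable cotinine levels in urine", with the caveat that the metabolite is short-lived.

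**Use of the score.** Section 5.2 defines the per-protocol set as completers with median compliance of at least 80%, or else splits at the median, and uses the score as a covariate. Section 6.4.3 has "per protocol, if at least 30 individuals have a cumulative compliance score of more than 80" per cent.

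**Smoking endpoint.** Section 5.4.2 lists current smoking (yes/no), "cigarettes in the last 7 days" and nicotine replacement use. Section 6.5.3 treats current smoking as a "binary response, can be analysed using a generalised estimation equation or generalised linear mixed model". Neither section names a data source or mentions cotinine. Smoking status at the end of the intervention (6.4.2) and in model 2 (6.4.4) is likewise not tied to cotinine.

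**The concern.** The reports go to coaches. Section 3.3 provides weekly one-to-one coaching to limit attrition, and section 3.8 makes the study open-label. A woman may find it hard to admit a lapse in that setting, so under-reporting is plausible. The SAP collects a biochemical measure that could detect some of it, but does not say what a positive result changes.

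The score depends on reports only, so a woman who reports full abstinence scores 100% whatever her cotinine shows. Unless someone intervenes, she enters the per-protocol set. Any intervention would be decided once results are visible, because no rule exists beforehand.

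Two results are at stake. One is the quit proportion, which readers will use to judge whether the programme worked. The other is the per-protocol change in the methylation scores, which is meant to show what real cessation does. Section 3.6 says the study serves to define effect sizes for later, larger studies, so a diluted estimate would carry forward into their planning.

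**Working it through.** **1. Where cotinine enters.**

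| Item | SAP section | Built from | Cotinine used? |
|---|---|---|---|
| Compliance score | 3.4 | reported compliant days | concordance check only |
| Per-protocol set, median split, covariate | 5.2, 5.4.1, 6.4.3 | compliance score | no |
| Current smoking | 5.4.2, 6.5.3 | source not stated | no |
| Smoking status, plots and model 2 | 6.4.2, 6.4.4 | source not stated | no |
| Primary ITT test, baseline v month 6 | 5.2, 6.4.3 | all participants | not needed |

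**2. Reproducing the SAP's own figure.** Section 3.6 gives a difference of 0.2, SD 0.44, n = 60, alpha 0.05 and power 0.94. Read as a two-sided paired test, with 0.44 as the SD of the within-woman change:

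- n = (0.44 × (1.960 + 1.555) / 0.2)² = 59.8, so 60.
- Power at n = 60 is 0.941 (normal) or 0.934 (noncentral t).

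The stated figure reproduces, so 0.2 and 0.44 are used below.

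**3. Assumptions not in the SAP.** A share m of the self-reported per-protocol set still smokes, with m = 10-25%. These women keep a fraction f of the effect, with f = 0 or 0.5.

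**4. Dilution.** Mean change = 0.2 × (1 − m(1 − f)).

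- f = 0: 0.18 at m = 10%, 0.15 at m = 25%.
- f = 0.5: 0.19 at m = 10%, 0.175 at m = 25%.

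**5. Quit proportion.** True proportion = reported × (1 − m). If 24 of 60 (40%) report quitting, 2.4-6 of them would be misreporters and the true proportion would be 36-30%. The 40% is illustrative.

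**6. Power in a per-protocol set of 30, the SAP's minimum.** Two-sided noncentral t. With f = 0, mixing raises the SD to √(0.44² + 0.2² × m(1 − m)).

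| m | Misreporters kept, n = 30 | Misreporters removed |
|---|---|---|
| 0 | 0.67 | – |
| 10% | 0.57 | 0.62 (n = 27) |
| 20% | 0.47 | 0.57 (n = 24) |
| 25% | 0.43 | 0.53 (n = 22) |

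The right-hand column is what verification can deliver, a gain of about 0.05-0.10. It cannot restore 0.67, because removing women shrinks the set.

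With f = 0.5 there is no power gain. At n = 40 and m = 20%, with the SD held at 0.44, power is 0.713 with misreporters kept and 0.702 after removal (n = 32). The estimate is still diluted in that case, 0.18 against 0.20.

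**7. The minimum of 30.** Removing anyone from a set of exactly 30 takes it below the threshold. A set of 40 stays above it at m = 20% (n = 32) and reaches it at m = 25% (n = 30).

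**The case against.** The strongest defence is that the SAP does use cotinine. Section 3.4 commits to a concordance check and says what a compliant woman's result should look like. A reader might infer from the silence that follows that a discordant result changes nothing. The text does not say that. It leaves the consequence open, and that is the defect.

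A reader might also infer that the quit endpoint is simply the coach's report. This is not established. Sections 5.4.2 and 6.5.3 name no source, section 3.11 has hospital or research staff enter outcome data in the eCRF, and study doctors rate adherence separately. That rating, however, feeds no analysis set.

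A third tempting reading is that quitting is overstated and the effect diluted as a matter of fact. Both are the expected directions if women under-report, but the SAP contains no misreporting rate and the figures above are conditional on an assumed one.

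The defence is also right that cotinine is an imperfect arbiter. It reflects nicotine replacement and electronic cigarettes, both of which the SAP anticipates (5.4.1, 5.4.2), and it is short-lived. It could misclassify abstainers who use nicotine products and would miss earlier smoking. This limits the remedy, but it does not justify leaving discordance without a rule.

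Finally, the study is described as predominantly exploratory and its main test does not use smoking status or compliance. That bears on how serious the point is. It does not remove it.

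**Conclusion.** The point holds in a limited form. In the smoking sub-study the score that determines per-protocol membership, the median split and the compliance covariate is built from reported days. The cotinine check has no cut-off and no consequence, and cotinine is absent from the definition of current smoking.

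The size depends on the assumed 10-25% misreporting. With no effect in misreporters, the per-protocol change falls from 0.20 to 0.18-0.15, and an illustrative reported quit proportion of 40% would be 36-30% in truth. If misreporters keep half the effect, the change falls only to 0.19-0.175.

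A reader might infer that the primary result is compromised. It is not: the intention-to-treat paired comparison of baseline with month 6 does not use the classification. Nor would verification restore full power, since the smaller set offsets much of the gain. The case for change is less bias and a rule fixed in advance. The SAP should be amended, but this is not a fault in its main analysis.

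**What to change.** Amend sections 3.4, 5.2 and 6.5.3 as follows.

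- **Verified abstinence at a visit:** no cigarettes reported for the preceding 7 days and urine cotinine below an assay cut-off fixed before analysis.
- **Discordant results:** among women reporting no nicotine replacement and no electronic cigarettes, count a discordant woman as smoking in the endpoint and leave her out of the verified per-protocol set.
- **Nicotine-product users:** classify by self-report and flag as not verifiable by cotinine.
- **Missing cotinine:** state the rule.
- **Minimum of 30:** state whether it applies before or after verification.
- **Data source:** name the source of current smoking.
- **Reporting:** show self-reported and cotinine-verified results side by side.

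The cost is SAP wording and recoding, since the cotinine samples are already planned. The downsides are a lower reported quit proportion and a smaller per-protocol set. If the minimum is applied after verification, that set may fall below 30 and the analysis would then rest on the median split. Cotinine verifies only the days before each visit, so smoking between visits would still go undetected.

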#### 3.5 Randomisation

Eligible participants in the dietary intervention group will be randomised to one of the two interventions using a secure Excel sheet developed by the statistician. The randomisation strategy is menopause- and BMI-stratified block randomisation in blocks of 4. Participants within each block will be allocated to a treatment 1:1. Users (clinicians) will provide menopausal status and BMI group and treatment allocation is then provided. The allocated treatment arm is recorded in the eCRF (Askimed).

No randomisation will be conducted in the smoking cessation sub-study.

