#### 2. Dietary intervention (n = 120)

One-hundred and twenty women without significant prior medical history with a body mass index (BMI) between 25 and 35 will be recruited and aided to conduct 16:8 intermittent fasting (16 h fasting, 8 h window for food consumption each day). The window during which food can be consumed can be freely chosen by each participant Participants will be randomly allocated one of the following groups using age- and BMI-stratified block randomisation:

• Intermittent fasting (n = 60)

Intermittent fasting has been shown to convey a series of metabolic and health benefits, promoting longevity and reducing tumour incidence in animal models. Recent human studies suggest similar benefits in humans. We aim to assess whether intermittent fasting can improve a variety of health parameters.

• Intermittent fasting with ketogenic supplement (n = 60)Intermittent fasting may mediate its benefits via timing of feeding/circadian rhythms, caloric restriction, and/or, in part, by promoting nutritional ketosis via the absence of carbohydrates; promotion of ketosis has been shown to induce longevity in mice. Ketogenic supplements are already commonly used in dietary therapy for pediatric epilepsy, but have not been routinely used in other settings. We aim to assess whether ketogenic supplements may boost ketosis and further enhance the health benefits of intermittent fasting.

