#### 3.8 Blinding

This is an open-label study. While the study is in progress, access to results of key study outcomes will not be available to the research team, trial statisticians, or other research collaborators.

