# 4 Study population

#### 4.1 Eligibility

#### 4.1.1 Inclusion criteria

- 1. Women aged 30 to 60
- 2. Motivated to change their lifestyle
- 3. Smoking cessation:  $\geq 10$  cigarettes per day for at least the last five years
- 4. Dietary intervention: BMI between 25 and 35
- \* Should 3 and 4 apply, the participant will be allocated to the smoking cessation group.

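### A single block size of 4 in an open-label, single-centre study makes about a third of the supplement allocations deducible, and Sections 3.1 and 3.5 name different stratifiers

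*SAP*

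**What the plan says.** Section 3.5 sets the method for the dietary sub-study: "The randomisation strategy is menopause- and BMI-stratified block randomisation in blocks of 4". It adds "Participants within each block will be allocated to a treatment 1:1". Allocation is made "using a secure Excel sheet developed by the statistician", and the working procedure is "Users (clinicians) will provide menopausal status and BMI group and treatment allocation is then provided". No other block size is mentioned. The same section states "No randomisation will be conducted in the smoking cessation sub-study", so the two diet arms form the only randomised comparison.

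Section 3.1, under the dietary intervention (n = 120, 60 per arm), describes the same allocation as "using age- and BMI-stratified block randomisation".

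Section 3.1 calls the study single-centre, and Section 3.8 says "This is an open-label study". One inclusion criterion in Section 4.1.1 calls for judgement: "Motivated to change their lifestyle".

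The between-arm comparison appears as a subgroup analysis in Section 5.4.1, as an option in Section 6.4.3 for the primary endpoint, in Section 6.5.3 for BMI and body composition, and in Section 6.6.3 for the microbiome.

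**The concern.** With one known block size, past allocations reveal future ones. In an open-label study past allocations are visible to those treating the participants, and hiding the unused rows of the list does not change that. Someone who foresees the arm can bring forward, delay or decline a woman, and a criterion based on motivation leaves room to do so. The arms could then differ in motivation or expected adherence from the start.

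This matters because the study has no control group. Supplement versus no supplement is the one contrast that randomisation protects.

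The stratifier conflict is a separate matter. In women aged 30 to 60, age group and menopausal status are related but different variables. While the two sections disagree, a reader cannot tell which factors were balanced by design or which ones a between-arm model should carry.

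**Working it through.** **The plan's own figure.** The SAP gives no figure for predictability. Its only design figure is in Section 3.6: 60 participants, difference 0.2, SD 0.44, power 0.94, significance level 0.05 (taken as two-sided).

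- Within-group change: Φ(0.2/0.44 × √60 − 1.960) = Φ(3.521 − 1.960) = Φ(1.561) = 0.941. The stated 0.94 is reproduced.
- Two arms of 60, same SD: Φ(0.2/(0.44 × √(2/60)) − 1.960) = Φ(2.490 − 1.960) = Φ(0.530) = 0.70.

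The study was therefore sized for the before-after change and not for the randomised comparison. That limits how much rests on the allocation.

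**Predictability in a complete block.** Inputs from Section 3.5: block size 4, ratio 1:1. There are six equally likely orders: AABB, ABAB, ABBA, BAAB, BABA, BBAA. The observer knows the block size, sees the earlier allocations in the stratum, and guesses the arm that is behind (a coin toss when level).

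| Place in block | Probability the arm is certain | Probability of a correct guess |
|---|---|---|
| 1 | 0 | 1/2 |
| 2 | 0 | 4/6 = 2/3 |
| 3 | 2/6 = 1/3 (first two match) | 1/3 × 1 + 2/3 × 1/2 = 2/3 |
| 4 | 1 | 1 |
| Sum | 4/3 | 17/6 |

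Certain: (4/3)/4 = 33.3%, or 40 of 120. Guessed correctly: (17/6)/4 = 70.8%, or 85 of 120. The 40 are included in the 85.

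**Allowing for unfinished blocks.** The SAP does not define the BMI groups, so the number of strata is an assumption. The first row is exact (120 = 30 complete blocks). The others are simulated with equally likely strata and 2,000 repetitions.

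| Assumed strata | Certain | Of 120 | Guessed correctly |
|---|---|---|---|
| 1 | 33.3% | 40 | 70.8% |
| 4 | 31.9% | 38 | 70.2% |
| 6 | 31.3% | 38 | 69.9% |
| 9 | 30.2% | 36 | 69.4% |

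Four unequal strata (40, 30, 20 and 10%) also give 31.9% and 70.2%. Stratification lowers predictability only slightly.

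**Effect of varying the block size.** Four strata, size hidden, observer using only the running imbalance:

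- sizes 4 and 6: about 1% certain, 69% guessed correctly;
- sizes 4, 6 and 8: about 0.1% certain, 67% guessed correctly.

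The certain shares here are lower bounds, because an observer using the full history could deduce somewhat more.

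**Stratifiers side by side.** Section 3.1: age and BMI. Section 3.5: menopausal status and BMI, with menopausal status named again as the clinician's input. Both are current text. The between-arm methods do not settle the matter: Section 6.5.3 offers a Wilcoxon test of change or a mixed model with a supplement term, and names neither pair of stratifiers.

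**The case against.** The strongest reply is that the SAP describes a block size and not a breach of concealment. A reader might infer that the clinicians who enrol know allocations in advance. The text does not support that. It speaks only of clinicians as users of the sheet. It does not say that they recruit, that they know the block size, or that one person sees all allocations in a stratum. The sheet is called secure, and what it displays is not described. Section 3.5 randomises women already found eligible, and the arm appears only after the stratum is entered. Who holds the list and when the arm is released may be covered in the protocol, which is not at hand. All of this stands, so the percentages describe what could be deduced under stated conditions and not what happened.

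A reader might also infer that the damage could never be adjusted for because motivation is not measured. That is unsafe. Sections 3.3.2 and 3.3.3 mention an analysis of dietary behaviours and motivation at the start, and Section 5.4.2 lists self-efficacy before and after the intervention. No between-arm adjustment for either is specified, but the data may exist.

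Finally, the study is described as mainly exploratory, the null hypothesis in Section 3.7 is baseline against month 6, and the documents show no motive to steer women towards or away from a supplement. This limits the weight of the point. It does not remove it, because the weakness lies in a stated rule that is cheap to change. Nor does it touch the contradiction on stratifiers.

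**Conclusion.** The point holds in a limited form. With fixed 1:1 blocks of 4, about 30 to 33% of allocations (36 to 40 of 120) could be deduced with certainty, and about 71% guessed in complete blocks. This assumes an observer who knows the block size and follows allocations within each stratum, and 1 to 9 strata.

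A reader might take this as a threat to the main result. It is not: the primary paired analysis of baseline against month 6 does not use the randomisation. Only the comparison of supplement with no supplement is exposed, and that comparison is optional or a subgroup analysis.

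The disagreement between Sections 3.1 and 3.5 on the stratifiers needs no assumption. It is a contradiction in current text and must be resolved.

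**What to change.** 1. **Section 3.5, allocations not yet made.** Use permuted blocks of randomly varying size within strata, and keep the sizes out of any document that clinicians see. Cost: a new list from the statistician, a line of SAP text, and slightly larger possible imbalance in small strata. The gain is mainly the loss of certainty; guessing falls only to about 67 to 69%.
2. **Sections 3.1 and 3.5.** State one pair of stratifiers, namely the pair actually programmed in the sheet. Cost: one line.
3. **Between-arm analyses (Sections 5.4.1, 6.4.3, 6.5.3, 6.6.3).** Include those stratifiers as covariates or strata. Cost: a few model terms, or a stratified test in place of the simple Wilcoxon test.
4. **Allocations already made.** As a sensitivity check, compare baseline characteristics between arms separately for predictable and unpredictable block positions. This needs only the allocation list in order and the baseline data. With about 36 to 40 women in predictable positions it can be read only descriptively.
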